Appendix D: Table, Figure, Listing Layouts

Appendix D1: Study-Specific Shells for Section 14

14.1.1 Subject Disposition by Dosage/Vaccine, All Subjects

	CV7202 1 µg	CV7202 2 µg	CV7202 5 µg	Rabipur	Total
Subjects screened					N
Subjects enrolled					x
Subjects vaccinated	xx (xx.x%)	xx (xx.x%)	xx (xx.x%)	xx (xx.x%)	xx (xx.x%)
Subjects ongoing	xx (xx.x%)	xx (xx.x%)	xx (xx.x%)	xx (xx.x%)	xx (xx.x%)
Subjects completed	xx (xx.x%)	xx (xx.x%)	xx (xx.x%)	xx (xx.x%)	xx (xx.x%)
Subjects withdrawn	xx (xx.x%)	xx (xx.x%)	xx (xx.x%)	xx (xx.x%)	xx (xx.x%)
Safety Analysis Set ^[a]	xx (xx.x%)	xx (xx.x%)	xx (xx.x%)	xx (xx.x%)	xx (xx.x%)
Full analysis (FA) set ^[b]	xx (xx.x%)	xx (xx.x%)	xx (xx.x%)	xx (xx.x%)	xx (xx.x%)
Main reason for termination	Consent withdrawn Violation of in/ex criteria Continuation jeopardizes subject Adverse event Non-compliance Lost to follow-up Study terminated by sponsor Pregnancy Other	xx (xx.x%) xx (xx.x%)	xx (xx.x%) xx (xx.x%)	xx (xx.x%) xx (xx.x%)	xx (xx.x%) xx (xx.x%)

[a] Received at least 1 dose of CV7202 or Rabipur.

[b] All subjects of the Safety Analysis Set with baseline and at least 1 postbaseline VNT sample.

Percentages are based on the number of vaccinated subjects in each column.

PROGRAM SOURCE: tlf-###, DATA CUT OFF DATE: DDMMYYYY

RUN DATE: DDMMYYYY hh:mm

Programming note:

Subjects ongoing will only be displayed, if table is generated before end of the trial.

14.1.2 Subject Disposition by Dosage/Vaccine and Treatment Group, All Subjects

		CV7202 1x1 µg	CV7202 2x1 µg	CV7202 1x2 µg	CV7202 2x2 µg
Subjects screened					
Subjects enrolled					
Subjects vaccinated		xx (xx.x%)	xx (xx.x%)	xx (xx.x%)	xx (xx.x%)
Subjects ongoing		xx (xx.x%)	xx (xx.x%)	xx (xx.x%)	xx (xx.x%)
Subjects completed		xx (xx.x%)	xx (xx.x%)	xx (xx.x%)	xx (xx.x%)
Subjects withdrawn		xx (xx.x%)	xx (xx.x%)	xx (xx.x%)	xx (xx.x%)
Safety Analysis Set ^[a]		xx (xx.x%)	xx (xx.x%)	xx (xx.x%)	xx (xx.x%)
Full analysis (FA) set ^[b]		xx (xx.x%)	xx (xx.x%)	xx (xx.x%)	xx (xx.x%)
Main reason for termination	Consent withdrawn	xx (xx.x%)	xx (xx.x%)	xx (xx.x%)	xx (xx.x%)
	Violation of in/ex criteria	xx (xx.x%)	xx (xx.x%)	xx (xx.x%)	xx (xx.x%)
	Continuation jeopardizes subject	xx (xx.x%)	xx (xx.x%)	xx (xx.x%)	xx (xx.x%)
	Adverse event	xx (xx.x%)	xx (xx.x%)	xx (xx.x%)	xx (xx.x%)
	Non-compliance	xx (xx.x%)	xx (xx.x%)	xx (xx.x%)	xx (xx.x%)
	Lost to follow-up	xx (xx.x%)	xx (xx.x%)	xx (xx.x%)	xx (xx.x%)
	Study terminated by sponsor	xx (xx.x%)	xx (xx.x%)	xx (xx.x%)	xx (xx.x%)
	Pregnancy	xx (xx.x%)	xx (xx.x%)	xx (xx.x%)	xx (xx.x%)
	Other	xx (xx.x%)	xx (xx.x%)	xx (xx.x%)	xx (xx.x%)
		xx (xx.x%)	xx (xx.x%)	xx (xx.x%)	xx (xx.x%)

[a] Received at least 1 dose of CV7202 or Rabipur.

[b] All subjects of the Safety Analysis Set with baseline and at least 1 postbaseline VNT sample.

Percentages are based on the number of vaccinated subjects in each column.

PROGRAM SOURCE: tlf-###, DATA CUT OFF DATE: DDMMYYYY

RUN DATE: DDMMYYYY hh:mm

Programming note:

Subjects ongoing will only be displayed, if table is generated before end of the trial.

CureVac AG
CV-7202-104

Statistical Analysis Plan
24 February 2022

Sponsor
Protocol number

Clinical Study Report
Page x of y

14.1.3 Subject Number by Country and Site
Safety Analysis Set

	CV7202 1 µg (N = xx)	CV7202 2 µg (N = xx)	CV7202 5 µg (N = xx)	Rabipur (N = xx)	Total (N = xx)
Germany Site 1	xx (xx.x%)	xx (xx.x%)	xx (xx.x%)	xx (xx.x%)	xx (xx.x%)
Belgium Site 2	xx (xx.x%)	xx (xx.x%)	xx (xx.x%)	xx (xx.x%)	xx (xx.x%)

PROGRAM SOURCE: tlfc-###, DATA CUT OFF DATE: DDMMYYYY

RUN DATE: DDMMYYYY hh:mm

Sponsor
Protocol number

Clinical Study Report
Page x of y

14.1.4.1 Demographic Characteristics by Dosage/Vaccine, Safety Analysis Set

	CV7202 1 µg (N = xx)	CV7202 2 µg (N = xx)	CV7202 5 µg (N = xx)	Rabipur (N = xx)	Total (N = xx)
Age (years)					
n	xx	xx	xx	xx	xx
Mean (SD)	xx.x (xx.xx)	xx.x (xx.xx)	xx.x (xx.xx)	xx.x (xx.xx)	xx.x (xx.xx)
Median	xx.x	xx.x	xx.x	xx.x	xx.x
Min, Max	xx, xx	xx, xx	xx, xx	xx, xx	xx, xx
Gender					
Male	xx (xx.x%)	xx (xx.x%)	xx (xx.x%)	xx (xx.x%)	xx (xx.x%)
Female	xx (xx.x%)	xx (xx.x%)	xx (xx.x%)	xx (xx.x%)	xx (xx.x%)
Missing	x	x	x	x	x
Childbearing potential					
Childbearing potential	xx (xx.x%)	xx (xx.x%)	xx (xx.x%)	xx (xx.x%)	xx (xx.x%)
Postmenopausal	xx (xx.x%)	xx (xx.x%)	xx (xx.x%)	xx (xx.x%)	xx (xx.x%)
Surgically sterile	xx (xx.x%)	xx (xx.x%)	xx (xx.x%)	xx (xx.x%)	xx (xx.x%)
Not applicable (male subject)	x	x	x	x	x
Ethnic origin					
American Indian or Alaska Native	xx (xx.x%)	xx (xx.x%)	xx (xx.x%)	xx (xx.x%)	xx (xx.x%)
Asian	xx (xx.x%)	xx (xx.x%)	xx (xx.x%)	xx (xx.x%)	xx (xx.x%)
Black	xx (xx.x%)	xx (xx.x%)	xx (xx.x%)	xx (xx.x%)	xx (xx.x%)
Native Hawaiian or Other Pacific Islander	xx (xx.x%)	xx (xx.x%)	xx (xx.x%)	xx (xx.x%)	xx (xx.x%)
White	xx (xx.x%)	xx (xx.x%)	xx (xx.x%)	xx (xx.x%)	xx (xx.x%)
Other	xx (xx.x%)	xx (xx.x%)	xx (xx.x%)	xx (xx.x%)	xx (xx.x%)
Missing	x	x	x	x	x

PROGRAM SOURCE: tlf-###, DATA CUT OFF DATE: DDMMYYYY

RUN DATE: DDMMYYYY hh:mm

Sponsor
Protocol number

Clinical Study Report
Page x of y

14.1.4.2 Demographic Characteristics by Dosage/Vaccine and Treatment Group, Safety Analysis Set

	CV7202 1x1 µg (N=xx)	CV7202 2x1 µg (N=xx)	CV7202 1x2 µg (N=xx)	CV7202 2x2 µg (N=xx)
Age (years)				
n	xx	xx	xx	xx
Mean (SD)	xx.x (xx.xx)	xx.x (xx.xx)	xx.x (xx.xx)	xx.x (xx.xx)
Median	xx.x	xx.x	xx.x	xx.x
Min, Max	xx, xx	xx, xx	xx, xx	xx, xx
Gender				
Male	xx (xx.x%)	xx (xx.x%)	xx (xx.x%)	xx (xx.x%)
Female	xx (xx.x%)	xx (xx.x%)	xx (xx.x%)	xx (xx.x%)
Missing	x	x	x	x
Childbearing potential				
Childbearing potential	xx (xx.x%)	xx (xx.x%)	xx (xx.x%)	xx (xx.x%)
Postmenopausal	xx (xx.x%)	xx (xx.x%)	xx (xx.x%)	xx (xx.x%)
Surgically sterile	xx (xx.x%)	xx (xx.x%)	xx (xx.x%)	xx (xx.x%)
Not applicable (male subject)	x	x	x	x
Ethnic origin				
American Indian or Alaska Native	xx (xx.x%)	xx (xx.x%)	xx (xx.x%)	xx (xx.x%)
Asian	xx (xx.x%)	xx (xx.x%)	xx (xx.x%)	xx (xx.x%)
Black	xx (xx.x%)	xx (xx.x%)	xx (xx.x%)	xx (xx.x%)
Native Hawaiian or Other Pacific Islander	xx (xx.x%)	xx (xx.x%)	xx (xx.x%)	xx (xx.x%)
White	xx (xx.x%)	xx (xx.x%)	xx (xx.x%)	xx (xx.x%)
Other	xx (xx.x%)	xx (xx.x%)	xx (xx.x%)	xx (xx.x%)
Missing	x	x	x	x

PROGRAM SOURCE: tlf-###, DATA CUT OFF DATE: DDMMYYYY

RUN DATE: DDMMYYYY hh:mm

CureVac AG
CV-7202-104

Statistical Analysis Plan
24 February 2022

Sponsor
Protocol number

Clinical Study Report
Page x of y

14.1.4.3 Demographic Characteristics by Dosage/Vaccine, Full Analysis Set

Programming note:
Repeat table 14.1.4.1 for 14.1.4.3

CureVac AG
CV-7202-104

Statistical Analysis Plan
24 February 2022

Sponsor
Protocol number

Clinical Study Report
Page x of y

14.1.4.4 Demographic Characteristics by Dosage/Vaccine and Treatment Group, Full Analysis Set

Programming note:
Repeat table 14.1.4.2 for 14.1.4.4

14.1.5.1 Baseline Characteristics by Dosage/Vaccine, Safety Analysis Set

	CV7202 1 µg (N = xx)	CV7202 2 µg (N = xx)	CV7202 5 µg (N = xx)	Rabipur (N = xx)	Total (N = xx)
Height (cm)					
n	xx	xx	xx	xx	xx
Mean (SD)	xx.x (xx.xx)	xx.x (xx.xx)	xx.x (xx.xx)	xx.x (xx.xx)	xx.x (xx.xx)
Median	xx.x	xx.x	xx.x	xx.x	xx.x
Min, Max	xx, xx	xx, xx	xx, xx	xx, xx	xx, xx
Weight (kg)					
n	xx	xx	xx	xx	xx
Mean (SD)	xx.x (xx.xx)	xx.x (xx.xx)	xx.x (xx.xx)	xx.x (xx.xx)	xx.x (xx.xx)
Median	xx.x	xx.x	xx.x	xx.x	xx.x
Min, Max	xx, xx	xx, xx	xx, xx	xx, xx	xx, xx
BMI (kg/m²)					
n	xx	xx	xx	xx	xx
Mean (SD)	xx.x (xx.xx)	xx.x (xx.xx)	xx.x (xx.xx)	xx.x (xx.xx)	xx.x (xx.xx)
Median	xx.x	xx.x	xx.x	xx.x	xx.x
Min, Max	xx, xx	xx, xx	xx, xx	xx, xx	xx, xx

PROGRAM SOURCE: tlf-###, DATA CUT OFF DATE: DDMMYYYY

RUN DATE: DDMMYYYY hh:mm

Sponsor
Protocol number

Clinical Study Report
Page x of y

14.1.5.2 Baseline Characteristics by Dosage/Vaccine and Treatment Group, Safety Analysis Set

	CV7202 1x1 µg (N=xx)	CV7202 2x1 µg (N=xx)	CV7202 1x2 µg (N=xx)	CV7202 2x2 µg (N=xx)
Height (cm)				
n	xx	xx	xx	xx
Mean (SD)	xx.x (xx.xx)	xx.x (xx.xx)	xx.x (xx.xx)	xx.x (xx.xx)
Median	xx.x	xx.x	xx.x	xx.x
Min, Max	xx, xx	xx, xx	xx, xx	xx, xx
Weight (kg)				
n	xx	xx	xx	xx
Mean (SD)	xx.x (xx.xx)	xx.x (xx.xx)	xx.x (xx.xx)	xx.x (xx.xx)
Median	xx.x	xx.x	xx.x	xx.x
Min, Max	xx, xx	xx, xx	xx, xx	xx, xx
BMI (kg/m ²)				
n	xx	xx	xx	xx
Mean (SD)	xx.x (xx.xx)	xx.x (xx.xx)	xx.x (xx.xx)	xx.x (xx.xx)
Median	xx.x	xx.x	xx.x	xx.x
Min, Max	xx, xx	xx, xx	xx, xx	xx, xx

PROGRAM SOURCE: tlf-###, DATA CUT OFF DATE: DDMMYYYY

RUN DATE: DDMMYYYY hh:mm

CureVac AG
CV-7202-104

Statistical Analysis Plan
24 February 2022

Sponsor
Protocol number

Clinical Study Report
Page x of y

14.1.5.3 Baseline Characteristics by Dosage/Vaccine, Full Analysis Set

Programming note:
Repeat table 14.1.5.1 for 14.1.5.3

CureVac AG
CV-7202-104

Statistical Analysis Plan
24 February 2022

Sponsor
Protocol number

Clinical Study Report
Page x of y

14.1.5.4 Baseline Characteristics by Dosage/Vaccine and Treatment Group, Full Analysis Set

Programming note:
Repeat table 14.1.5.2 for 14.1.5.4

14.1.6 Concomitant Medications/Vaccinations by Dosage/Vaccine, Safety Analysis Set

ATC class Preferred Name [n (%)]	CV7202 1 µg (N = xx)	CV7202 2 µg (N = xx)	CV7202 5 µg (N = xx)	Rabipur (N = xx)	Total (N = xx)
Subjects receiving any ongoing or concomitant medications/vaccinations	xx (xx.x%)	xx (xx.x%)	xx (xx.x%)	xx (xx.x%)	xx (xx.x%)
ATC Class 1	xx (xx.x%)	xx (xx.x%)	xx (xx.x%)	xx (xx.x%)	xx (xx.x%)
Preferred Name 1	xx (xx.x%)	xx (xx.x%)	xx (xx.x%)	xx (xx.x%)	xx (xx.x%)
Preferred Name 2	xx (xx.x%)	xx (xx.x%)	xx (xx.x%)	xx (xx.x%)	xx (xx.x%)
.					
ATC Class 2	xx (xx.x%)	xx (xx.x%)	xx (xx.x%)	xx (xx.x%)	xx (xx.x%)
Preferred Name 1	xx (xx.x%)	xx (xx.x%)	xx (xx.x%)	xx (xx.x%)	xx (xx.x%)
Preferred Name 2	xx (xx.x%)	xx (xx.x%)	xx (xx.x%)	xx (xx.x%)	xx (xx.x%)
.					

Note: At each level of summation (overall, ATC class, preferred name), subjects reporting more than 1 medication / vaccination are counted only once.

Table is sorted by descending total subject count on the ATC level.

Percentages are based on total no. of subjects in each treatment group.

Terms were coded using WHODrug Global B3 format, Sep2021 release.

PROGRAM SOURCE: tlf-###, DATA CUT OFF DATE: DDMMYYYY

RUN DATE: DDMMYYYY hh:mm

14.2.1.1 Rabies Specific VNTs >= 0.5 IU/ml by Dosage/Vaccine, Full Analysis Set

		CV7202 1 µg (N = xx)	CV7202 2 µg (N = xx)	CV7202 5 µg (N = xx)	Rabipur (N = xx)
VNTs >= 0.5 IU/ml					
V3 (Day 1)	n	xx	xx	xx	xx
	No	xx (xx.x%)	xx (xx.x%)	xx (xx.x%)	xx (xx.x%)
	Yes	xx (xx.x%)	xx (xx.x%)	xx (xx.x%)	xx (xx.x%)
	95% CI	(xx.x, xx.x)	(xx.x, xx.x)	(xx.x, xx.x)	(xx.x, xx.x)
V5 (Day 8)	n	xx	xx	xx	xx
	No	xx (xx.x%)	xx (xx.x%)	xx (xx.x%)	xx (xx.x%)
	Yes	xx (xx.x%)	xx (xx.x%)	xx (xx.x%)	xx (xx.x%)
	95% CI	(xx.x, xx.x)	(xx.x, xx.x)	(xx.x, xx.x)	(xx.x, xx.x)
V7 (Day 15)	..				
V8 (Day 29)					
V10 (Day 36)					
V11 (Day 43)					
V12 (Day 57)					
V13 (Day 91)					
V14 (Month 6)					
V15 (Month 12)					
V16 (Month 18)					
V17 (Trial End/Month 24)					

CI = Confidence interval (exact Clopper-Pearson confidence interval) for category yes.

VNT >= 0.5 IU/mL = virus neutralization titer threshold according to WHO guideline.

PROGRAM SOURCE: tlfl-###, DATA CUT OFF DATE: DDMMYYYY

RUN DATE: DDMMYYYY hh:mm

Sponsor

Clinical Study Report

Protocol number

Page x of y

14.2.1.2 Rabies Specific VNTs >= 0.5 IU/ml by Dosage/Vaccine and Treatment Group, Full Analysis Set

	CV7202 1x1 µg (N = xx)	CV7202 2x1 µg (N = xx)	CV7202 1x2 µg (N = xx)	CV7202 2x2 µg (N = xx)	
VNTs >= 0.5 IU/ml					
V3 (Day 1)	n No Yes 95% CI	xx xx (xx.x%) xx (xx.x%) (xx.x, xx.x)			
V5 (Day 8)	n No Yes 95% CI	xx xx (xx.x%) xx (xx.x%) (xx.x, xx.x)			
V7 (Day 15)					
V8 (Day 29)					
V10 (Day 36)					
V11 (Day 43)					
V12 (Day 57)					
V13 (Day 91)					
V14 (Month 6)					
V15 (Month 12)					
V16 (Month 18)					
V17 (Trial End/Month 24)					

CI = Confidence interval (exact Clopper-Pearson confidence interval) for category yes.

VNT >= 0.5 IU/mL = virus neutralization titer threshold according to WHO guideline.

PROGRAM SOURCE: tlfl-###, DATA CUT OFF DATE: DDMMYYYY

RUN DATE: DDMMYYYY hh:mm

14.2.1.3 Rabies Specific VNTs (IU/mL) by Dosage/Vaccine, Full Analysis Set

	CV7202 1 µg (N = xx)	CV7202 2 µg (N = xx)	CV7202 5 µg (N = xx)	Rabipur (N = xx)
V3 (Day 1)	n xx	xx	xx	xx
	GMT (SD) xx.x (xx.xx)	xx.x (xx.xx)	xx.x (xx.xx)	xx.x (xx.xx)
	95% CL (xx.x, xx.x)	(xx.x, xx.x)	(xx.x, xx.x)	(xx.x, xx.x)
	Median xx.x	xx.x	xx.x	xx.x
	Min, Max xx, xx	xx, xx	xx, xx	xx, xx
V5 (Day 8)	n xx	xx	xx	xx
	GMT (SD) xx.x (xx.xx)	xx.x (xx.xx)	xx.x (xx.xx)	xx.x (xx.xx)
	95% CL (xx.x, xx.x)	(xx.x, xx.x)	(xx.x, xx.x)	(xx.x, xx.x)
	Median xx.x	xx.x	xx.x	xx.x
	Min, Max xx, xx	xx, xx	xx, xx	xx, xx
V7 (Day 15)	..			
V8 (Day 29)				
V10 (Day 36)				
V11 (Day 43)				
V12 (Day 57)				
V13 (Day 91)				
V14 (Month 6)				
V15 (Month 12)				
V16 (Month 18)				
V17 (Trial End/Month 24)				

GMT = Geometric mean titer, CL = Confidence limit.

Data are log-transformed, mean, SD and 95% CLs calculated and antilog of mean, SD and 95% CLs tabulated.

Titers marked as below lower limit of quantification (LLOQ=0.1 IU/mL) are set to 0.5*LLOQ.

PROGRAM SOURCE: tlf-###, DATA CUT OFF DATE: DDMMYYYY

RUN DATE: DDMMYYYY hh:mm

Sponsor

Clinical Study Report
Page x of y

Protocol number

14.2.1.4 Rabies Specific VNTs (IU/mL) by Dosage/Vaccine and Treatment Group, Full Analysis Set

	CV7202 1x1 µg (N = xx)	CV7202 2x1 µg (N = xx)	CV7202 1x2 µg (N = xx)	CV7202 2x2 µg (N = xx)
V3 (Day 1)	n xx	xx	xx	xx
	GMT (SD) xx.x (xx.xx)	xx.x (xx.xx)	xx.x (xx.xx)	xx.x (xx.xx)
	95% CL (xx.x, xx.x)	(xx.x, xx.x)	(xx.x, xx.x)	(xx.x, xx.x)
	Median xx.x	xx.x	xx.x	xx.x
	Min, Max xx, xx	xx, xx	xx, xx	xx, xx
V5 (Day 8)	n xx	xx	xx	xx
	GMT (SD) xx.x (xx.xx)	xx.x (xx.xx)	xx.x (xx.xx)	xx.x (xx.xx)
	95% CL (xx.x, xx.x)	(xx.x, xx.x)	(xx.x, xx.x)	(xx.x, xx.x)
	Median xx.x	xx.x	xx.x	xx.x
	Min, Max xx, xx	xx, xx	xx, xx	xx, xx
V7 (Day 15)	..			
V8 (Day 29)				
V10 (Day 36)				
V11 (Day 43)				
V12 (Day 57)				
V13 (Day 91)				
V14 (Month 6)				
V15 (Month 12)				
V16 (Month 18)				
V17 (Month 24)				

GMT = Geometric mean titer, CL = Confidence limit.

Data are log-transformed, mean, SD and 95% CLs calculated and antilog of mean, SD and 95% CLs tabulated.

Titters marked as below lower limit of quantification (LLOQ=0.1 IU/mL) are set to 0.5*LLOQ.

PROGRAM SOURCE: tlf-###, DATA CUT OFF DATE: DDMMYYYY

RUN DATE: DDMMYYYY hh:mm

Sponsor
Protocol number

Clinical Study Report
Page x of y

14.2.2.1.1 RABV-G Specific Levels of IgM >= 780 U/ml by Dosage/Vaccine, Full Analysis Set

		CV7202 1 µg (N = xx)	CV7202 2 µg (N = xx)	CV7202 5 µg (N = xx)	Rabipur (N = xx)
IgM >= 780 U/ml					
V3 (Day 1)	n	xx	xx	xx	xx
	No	xx (xx.x%)	xx (xx.x%)	xx (xx.x%)	xx (xx.x%)
	Yes	xx (xx.x%)	xx (xx.x%)	xx (xx.x%)	xx (xx.x%)
	95% CI	(xx.x, xx.x)	(xx.x, xx.x)	(xx.x, xx.x)	(xx.x, xx.x)
V5 (Day 8)	n	xx	xx	xx	xx
	No	xx (xx.x%)	xx (xx.x%)	xx (xx.x%)	xx (xx.x%)
	Yes	xx (xx.x%)	xx (xx.x%)	xx (xx.x%)	xx (xx.x%)
	95% CI	(xx.x, xx.x)	(xx.x, xx.x)	(xx.x, xx.x)	(xx.x, xx.x)
V7 (Day 15)	..				
V8 (Day 29)					
V10 (Day 36)					
V11 (Day 43)					
V12 (Day 57)					
V13 (Day 91)					
V14 (Month 6)					
V15 (Month 12)					

CI = Confidence interval (exact Clopper-Pearson confidence interval) for category yes.

PROGRAM SOURCE: tlif-###, DATA CUT OFF DATE: DDMMYYYY

RUN DATE: DDMMYYYY hh:mm

Sponsor

Clinical Study Report

Protocol number

Page x of y

14.2.2.1.2 RABV-G Specific Levels of IgM >= 780 U/ml by Dosage/Vaccine and Treatment Group, Full Analysis Set

	CV7202 1x1 µg (N = xx)	CV7202 2x1 µg (N = xx)	CV7202 1x2 µg (N = xx)	CV7202 2x2 µg (N = xx)	
IgM >= 780 U/ml					
V3 (Day 1)	n No Yes 95% CI	xx xx (xx.x%) xx (xx.x%) (xx.x, xx.x)			
V5 (Day 8)	n No Yes 95% CI	xx xx (xx.x%) xx (xx.x%) (xx.x, xx.x)			
V7 (Day 15)	..				
V8 (Day 29)					
V10 (Day 36)					
V11 (Day 43)					
V12 (Day 57)					
V13 (Day 91)					
V14 (Month 6)					
V15 (Month 12)					

CI = Confidence interval (exact Clopper-Pearson confidence interval) for category yes.

PROGRAM SOURCE: tlfc-###, DATA CUT OFF DATE: DDMMYYYY

RUN DATE: DDMMYYYY hh:mm

14.2.2.1.3 RABV-G Specific Levels of IgM (U/mL) by Dosage/Vaccine, Full Analysis Set

	CV7202 1 µg (N = xx)	CV7202 2 µg (N = xx)	CV7202 5 µg (N = xx)	Rabipur (N = xx)
V3 (Day 1)	n xx	xx	xx	xx
	GMT (SD) xx.x (xx.xx)	xx.x (xx.xx)	xx.x (xx.xx)	xx.x (xx.xx)
	95% CL (xx.x, xx.x)	(xx.x, xx.x)	(xx.x, xx.x)	(xx.x, xx.x)
	Median xx.x	xx.x	xx.x	xx.x
	Min, Max xx, xx	xx, xx	xx, xx	xx, xx
V5 (Day 8)	n xx	xx	xx	xx
	GMT (SD) xx.x (xx.xx)	xx.x (xx.xx)	xx.x (xx.xx)	xx.x (xx.xx)
	95% CL (xx.x, xx.x)	(xx.x, xx.x)	(xx.x, xx.x)	(xx.x, xx.x)
	Median xx.x	xx.x	xx.x	xx.x
	Min, Max xx, xx	xx, xx	xx, xx	xx, xx
V7 (Day 15)	..			
V8 (Day 29)				
V10 (Day 36)				
V11 (Day 43)				
V12 (Day 57)				
V13 (Day 91)				
V14 (Month 6)				
V15 (Month 12)				

GMT = Geometric mean titer, CL = Confidence limit.

Data are log-transformed, mean, SD and 95% CLs calculated and antilog of mean, SD and 95% CLs tabulated.

Titers marked as below lower limit of quantification (LLOQ=780 U/mL) are set to 0.5*LLOQ.

PROGRAM SOURCE: tlfl-###, DATA CUT OFF DATE: DDMMYYYY

RUN DATE: DDMMYYYY hh:mm

Programming note:

Number of decimals will vary by lab parameter - in general present mean, median to 1 decimal more than individual data, SD to 2 decimals more than individual data. Refer to SAP.

Sponsor

Clinical Study Report

Page x of y

Protocol number

14.2.2.1.4 RABV-G Specific Levels of IgM (U/mL) by Dosage/Vaccine and Treatment Group, Full Analysis Set

	CV7202 1x1 µg (N = xx)	CV7202 2x1 µg (N = xx)	CV7202 1x2 µg (N = xx)	CV7202 2x2 µg (N = xx)
V3 (Day 1)	n xx	xx	xx	xx
	GMT (SD) xx.x (xx.xx) (xx.x, xx.x)	xx.x (xx.xx) (xx.x, xx.x)	xx.x (xx.xx) (xx.x, xx.x)	xx.x (xx.xx) (xx.x, xx.x)
	95% CL xx.x, xx.x	xx.x, xx.x	xx.x, xx.x	xx.x, xx.x
	Median xx.x	xx.x	xx.x	xx.x
	Min, Max xx, xx	xx, xx	xx, xx	xx, xx
V5 (Day 8)	n xx	xx	xx	xx
	GMT (SD) xx.x (xx.xx) (xx.x, xx.x)	xx.x (xx.xx) (xx.x, xx.x)	xx.x (xx.xx) (xx.x, xx.x)	xx.x (xx.xx) (xx.x, xx.x)
	95% CL xx.x, xx.x	xx.x, xx.x	xx.x, xx.x	xx.x, xx.x
	Median xx.x	xx.x	xx.x	xx.x
	Min, Max xx, xx	xx, xx	xx, xx	xx, xx
V7 (Day 15)	..			
V8 (Day 29)				
V10 (Day 36)				
V11 (Day 43)				
V12 (Day 57)				
V13 (Day 91)				
V14 (Month 6)				
V15 (Month 12)				

GMT = Geometric mean titer, CL = Confidence limit.

Data are log-transformed, mean, SD and 95% CLs calculated and antilog of mean, SD and 95% CLs tabulated.

Titers marked as below lower limit of quantification (LLOQ=780 U/mL) are set to 0.5*LLOQ.

PROGRAM SOURCE: tlfc-##, DATA CUT OFF DATE: DDMMYYYY

RUN DATE: DDMMYYYY hh:mm

Programming note:

Number of decimals will vary by lab parameter - in general present mean, median to 1 decimal more than individual data, SD to 2 decimals more than individual data. Refer to SAP.

CureVac AG
CV-7202-104

Statistical Analysis Plan
24 February 2022

Sponsor
Protocol number

Clinical Study Report
Page x of y

14.2.2.2.1 RABV-G Specific Levels of IgA >=195.5 U/ml by Dosage/Vaccine, Full Analysis Set

Programming note:
Repeat table 14.2.2.1.1 for 14.2.2.2.1

CureVac AG
CV-7202-104

Statistical Analysis Plan
24 February 2022

Sponsor
Protocol number

Clinical Study Report
Page x of y

14.2.2.2.2 RABV-G Specific Levels of IgA ≥ 195.5 U/ml by Dosage/Vaccine and Treatment Group, Full Analysis Set

Programming note:
Repeat table 14.2.2.1.2 for 14.2.2.2.2

14.2.2.2.3 RABV-G Specific Levels of IgA (U/mL) by Dosage/VaccineVisit, Full Analysis Set

Programming note:

Repeat table 14.2.2.1.3 for 14.2.2.2.3

Number of decimals will vary by lab parameter - in general present mean, median to 1 decimal more than individual data, SD to 2 decimals more than individual data. Refer to SAP.

14.2.2.2.4 RABV-G Specific Levels of IgA (U/mL) by Dosage/Vaccine and Treatment Group, Full Analysis Set

Programming note:

Repeat table 14.2.2.1.4 for 14.2.2.2.4

Number of decimals will vary by lab parameter - in general present mean, median to 1 decimal more than individual data, SD to 2 decimals more than individual data. Refer to SAP.

14.2.2.3.1 RABV-G Specific Levels of IgG >=780 U/ml by Dosage/Vaccine, Full Analysis Set

Programming note:

Repeat table 14.2.2.1.1 for 14.2.2.3.1 IgG, including V16 (Month 18) and V17 (Month 24) data of subjects with detectable RABV-G specific IgG at 6 months after the last vaccination.

Sponsor
Protocol number

Clinical Study Report
Page x of y

14.2.2.3.2 RABV-G Specific Levels of IgG >=780 U/ml by Dosage/Vaccine and Treatment Group, Full Analysis Set

Programming note:

Repeat table 14.2.2.1.2 for 14.2.2.3.2 IgG, including V16 (Month 18) and V17 (Month 24) data of subjects with detectable RABV-G specific IgG at 6 months after the last vaccination.

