4.2 Endpoints

Primary Endpoints:

- The percentages of subjects with, and the frequencies and intensities of solicited local adverse events (AEs) reported on the day of vaccination and the 7 subsequent days (Days 1-8).
- The percentages of subjects with, and the frequencies, intensities and relationship to vaccination, of solicited systemic AEs reported on the day of vaccination and the 7 subsequent days (Days 1-8).
- The duration (in days) of solicited local AE, of solicited systemic AE and of the individual solicited AEs.
- The percentages of subjects with and frequencies and intensities of any unsolicited and related unsolicited AEs reported on the day of vaccination and the 28 subsequent days (Days 1-29).
- The percentages of subjects with and frequencies and relationship to vaccination, of any serious adverse events (SAEs) and any MAAEs up to 12 months post last dose.
- The percentages of subjects with and frequencies and relationship to vaccination of any adverse events of special interest (AESIs) up to 12 months post vaccination.

Secondary Endpoints:

For safety

- The percentages of subjects with and frequencies of SAEs and MAAEs related to study vaccination from 12 months post last dose up to 24 months post last dose (trial end).
- The percentages of subjects with and frequencies and relationship to vaccination of any AESIs from 12 months post last dose up to 24 months post last dose (trial end).

For the characterization of the humoral immune response

- Percentages of subjects with rabies-specific serum VNTs ≥ 0.5 IU/ml by trial group on Days 1 (pre-vaccination), 15, 43, and 12, 18* and 24* months post last dose.
- Serum geometric mean titers (GMTs) of VNTs by trial group on Days 1, 8, 15, 29, 36, 43, 57, 91, and 6 and 12, 18* and 24* months post-last dose.

* Will be performed only in subjects with detectable RABV-G-specific IgG at 6 months after the last vaccination or Day 91 if the Month 6 blood sample is not available.

Exploratory Endpoints:

For the evaluation of the innate immune response:

- Serum cytokine concentrations* including but not limited to CXCL10, CCL3, IL-6, TNF- α and IFN- γ , at pre-vaccination and 4 hours post-vaccination on Day 1, and Days 2 or 3** and 8 after each vaccination.
- Transcriptome profiling* on the day of vaccination at pre-vaccination, and Days 2 or 3** and 8 after each vaccination.

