* Will be performed in the first 5 subjects in Group 2 (** on Day 3) and all subjects in Groups 3 and 4 (** on Day 2). Note that Day 3 was planned in the original protocol and only applies to subjects in Groups 1 and 2 who were already enrolled and vaccinated before this protocol amendment was issued. Day 2 applies to all other subjects.

For the evaluation of antigen specific T-cell response:

- The frequencies and functionalities of RABV-G-specific T cells in peripheral blood from the first 5 subjects in Group 2 and all subjects in Groups 3 and 4 on Days 1, 8, 36, 91*, and 6* and 12* months post-last dose.

* For groups that have shown a significant T-cell response at Day 8 or 36 compared to baseline.

For the evaluation and characterization of the B cell response

- The frequencies of RABV-G-specific B cells in peripheral blood from the first 5 subjects in Group 2 and all subjects in Groups 3 and 4 on Days 1, 8, 36, 91*, and 6* and 12* months post-last dose.
- The frequencies and activation status of phenotypically distinct subsets of B cell populations, including but not limited to naïve and memory B cells, plasmablasts and plasma cells for the first 5 subjects in Group 2 and all subjects in Groups 3 and 4 on Days 1, 8, 36, 91*, and 6* and 12* months post-last dose.
- Sequencing of B-cell receptors (BCR) of circulating B cells on Days 1, 8, 29, 36, 57, 91*, and 6* and 12* months post-last dose.

* For groups that have shown a significant B-cell response at Day 8 or 36 compared to baseline.

For the characterization of the humoral immune response:

- RABV-G-specific IgM, IgG and IgA levels measured by ELISA on Days 1, 8, 15, 29, 36, 43, 57, 91, and 6 and 12 months post-last dose.
- RABV-G-specific IgG levels measured by ELISA 18* and 24* months post-last dose.
- Identification of epitopes recognized by vaccine-induced antibodies on Days 1, 15, 43, and 2, 6 and 12 months post-last dose**.
- Measurement of RABV-G-specific antibody avidity and affinity on Days 1, 15, 43, and 2, 6 and 12 months post-last dose**.

- Measurement of VNTs against additional heterologous lyssaviruses on Days 1, 15, 43, and 2, 6 and 12 months post-last dose**.

* Will be performed only in subjects with detectable RABV-G-specific IgG at 6 months after the last vaccination or Day 91 if the Month 6 blood sample is not available.

[figure not shown]
** Will be performed only on selected samples with VNT >0.5 IU/ml.

5 Trial Design

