9.3 Immunogenicity Assessments

The following immunogenicity assessments will be made:

Rabies-specific serum VNTs will be measured using the WHO-recommended rapid fluorescent foci inhibition test (RFFIT) before and after vaccination on Days 1, 8, 15, 29, 36, 43, 57, 91, and 6, 12, 18 and 24 months post-last dose.

The percentages of vaccine recipients with VNTs ≥ 0.5 IU/ml (WHO-recommended threshold correlating with protective immune responses) will be determined for each trial group. An antibody titer of 0.5 IU/ml serum is viewed as a surrogate of protection and defines seroconversion [26]. GMTs by treatment group will be calculated based on the VNTs on Days 1, 8, 15, 29, 36, 43, 57, 91, and 6, 12, 18 and 24 months post-last dose. VNTs assessments will be performed in a GCP-compliant laboratory.

Note that VNTs assessments at 18 and 24 months after the last vaccination will only be performed in subjects with detectable RABV-G-specific IgG at 6 months after the last vaccination or Day 91 if the Month 6 blood sample is not available.

RABV-G-specific IgM, IgG and IgA serum antibody levels will be measured by enzyme-linked immunosorbent assay (ELISA) on Days 1, 8, 15, 29, 36, 43, 57, 91, and 6 and 12 months post-last dose. In addition, RABV-G-specific IgG serum antibody levels will be measured at 18 and 24 months after the last vaccination in subjects with detectable RABV-G-specific IgG at 6 months after the last vaccination or Day 91 if the Month 6 blood sample is not available.

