Visit 15A may be conducted only in case Visit 15 was conducted as a phone call, and when restrictive measures related to COVID-19 no longer prevent site visits, and the window of Visit 15 has expired. Visit 15A allows the trial procedures, including the blood draws for safety and immunogenicity testing, to occur during a widened visit window starting the day after the expiry of the original visit window and lasting up to 3 months after the original projected visit date (+31-90 days). In that case, all procedures as described in Section 9.4.17.1 for Visit 15, including and blood sampling for safety and immunogenicity assessments, should be performed at Visit 15A.

Also, in case Visit 15 was conducted on site but not all procedures could be performed, Visit 15A should be scheduled on site within the protocol-allowed time interval for Visit 15A (+31-90 days).

If no blood sampling could be performed at Visit 15 and 15A, the end-of-trial blood sample for safety assessment may be performed at Visit 17 (Month 24: Day 729).

9.4.18 *Visit 16 (Month 18: Day 547)*

9.4.18.1 *Visit 16*

The following activities will be performed during Visit 16:

- Safety assessments (SAEs related to study vaccination, MAAEs related to study vaccination, intercurrent medical conditions, AESIs and concomitant medications and vaccinations).
- Blood draw for immunogenicity (only in subjects with detectable RABV-G-specific IgG at 6 months after the last vaccination or Day 91 if the Month 6 blood sample is not available) – VNTs (~18 ml), IgG (~6 ml) (section 9.5.3).

In case Visit 16 cannot take place on site due to the public health emergency related to COVID-19, safety information should be collected via a phone call within the protocol-allowed time interval for Visit 16 (± 30 days).

9.4.18.2 *Optional Visit 16A*

Visit 16A may be conducted only in case Visit 16 was conducted as a phone call, and when restrictive measures related to COVID-19 no longer prevent site visits, and the window of Visit 16 has expired. Visit 16A allows the trial procedures, including the blood draws for immunogenicity testing, to occur during a widened visit window starting the day after the expiry of the original visit window and lasting up to 3 months after the original projected visit date (+31-90 days). In that case, all procedures as described in

Section 9.4.16.1 for Visit 16, including blood sampling for immunogenicity assessment, should be performed at Visit 16A.

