10.1 Immunogenicity Endpoints and Variables

10.1.1 Secondary Immunogenicity Endpoint

For the characterization of the humoral immune response

- Percentages of subjects with Rabies Specific serum VNTs ≥ 0.5 IU/ml by trial group on Days 1 (pre-vaccination), 15 and 43 and 12, 18*, and 24* months after the last dose.
- Serum geometric mean titers (GMTs) of VNTs by trial group on Days 1, 8, 15, 29, 36, 43, 57, and 91 and 6, 12, 18*, and 24* months after the last dose.

* Will be performed only in subjects with detectable RABV-G-specific IgG at 6 months after the last vaccination.

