10.3 Exploratory Analyses

10.3.1 Immunoglobulin

The number and percentage of subjects with detectable RABV-G-specific immunoglobulin ($> \text{LLOQ}$: IgM $\geq 780 \text{ U/ml}$, IgA $\geq 195.5 \text{ U/ml}$ and IgG $\geq 780 \text{ U/ml}$) levels will be determined for each visit and displayed by vaccination group and dose regimen including 95% exact confidence limits. The percentages will be based on subjects providing data for the respective visit.

For evaluation of values below the limit of quantification (=BLQ values) for tables and figures, the following conventions will be made:

- Values <LLOQ are identified as BLQ values.
- All concentration values marked as BLQ will be set to $0.5 * \text{LLOQ}$ (LLOQs: IgM 780 U/ml, IgA 195.5 U/ml, IgG $\geq 780 \text{ U/ml}$)
- Missing post-dose values will not be replaced.

Absolute (raw untransformed) RABV-G-specific IgM, IgG and IgA levels will be summarized for each visit by vaccination group and dose regimen.

RABV-G-specific immunoglobulin levels will be log-transformed and the mean and 95% confidence interval of the log-transformed values will be calculated. The GMTs (= antilog mean of log-transformed data) and the corresponding 95% confidence intervals for the GMTs (=antilog lower and upper 95% confidence bound of log-transformed data) as well as geometric SD, median, minimum and maximum will be tabulated by vaccination group and dose regimen for baseline and each postbaseline visit.

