12. CHANGES TO PROTOCOL-SPECIFIED ANALYSES

The protocol defines 2 PP sets as subsets of the FA set. Due to the small number of subjects per treatment group, it was decided that no per-protocol sets will be defined and used for analysis.

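### The SAP's Month 18/24 selection rule omits the protocol's Day 91 fallback without declaring it, so the IgG table notes, if programmed as a filter, would leave out subjects the protocol has bled

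*SAP*

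**What the plan says.** **Protocol.** Section 4.2 limits Month 18 and 24 antibody testing to subjects with "detectable RABV-G-specific IgG at 6 months after the last vaccination or Day 91 if the Month 6 blood sample is not available". The same two-part rule appears in the synopsis, the notes to Tables 2.1 and 9.3, section 9.3, and the blood-draw instructions for Visit 16 (9.4.18.1) and Visit 17 (9.4.19.1). It therefore governs who is actually bled.

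**SAP, endpoint sections.** The footnotes in 10.1.1 (VNT) and 10.1.2 (IgG) read "Will be performed only in subjects with detectable RABV-G-specific IgG at 6 months after the last vaccination" and stop there.

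**SAP, table shells.** The programming notes to 14.2.2.3.1 through 14.2.2.3.4 extend the IgM templates by "including V16 (Month 18) and V17 (Month 24) data of subjects with detectable RABV-G specific IgG at 6 months after the last vaccination". Again there is no Day 91 alternative. The VNT shells (14.2.1.1 to 14.2.1.4) list Months 18 and 24 with no comparable note.

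**SAP, general rule.** For immunoglobulin percentages, section 10.3.1 says "The percentages will be based on subjects providing data for the respective visit".

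**SAP, declared changes.** Section 12 starts "The protocol defines 2 PP sets as subsets of the FA set" and reports that these sets are not used. It lists no other change. Section 2 names protocol version 2.0 of 30 April 2020 as the source, and section 7 includes the COVID-19 make-up visits.

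**The concern.** The protocol foresaw missing Month 6 samples. Visit 14 may become a phone call because of COVID-19 (9.4.16.1), and Visit 14A goes ahead only once restrictions allow it. The Day 91 alternative keeps subjects with a missing Month 6 result in the persistence follow-up.

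The SAP notes tell the programmer whose Month 18 and 24 IgG results go into the tables. Taken literally, they omit a subject who qualified through Day 91, although that subject's blood was drawn and tested under the protocol. The late IgG rows would then rest on fewer subjects than were measured. They could also describe a different set of people from the VNT rows for the same regimen. Because the SAP's general rule points the other way, two programmers could produce different tables from the same document.

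**Working it through.** Neither document has a sample-size or power figure to reproduce. The check is a comparison of texts, followed by an illustration.

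**Step 1: the two rules applied to each type of subject**

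| Month 6 sample | IgG result | Bled at Months 18/24 (protocol) | In late IgG rows, note read as a filter | In late IgG rows, SAP 10.3.1 |
|---|---|---|---|---|
| Available | Detectable at Month 6 | Yes | Yes | Yes |
| Available | Not detectable at Month 6 | No | No | No data |
| Missing | Detectable on Day 91 | Yes | **No** | Yes |
| Missing | Not detectable on Day 91 | No | No | No data |

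Only the third row differs. A subject must have no Month 6 sample, have detectable IgG on Day 91, and then be sampled at Month 18 or 24.

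**Step 2: what counts as a Month 6 sample.** Protocol 9.5 and Table 9.3 treat a Visit 14A draw (15 to 90 days after the planned date) as the Month 6 draw. SAP section 7 gives it a separate visit label, M6+3. The immunogenicity shells have no Visit 14A row, and the SAP does not say whether such a sample counts as Month 6 for selection. The size of the third row depends on that answer.

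**Step 3: illustration of size.** Inputs: 8 subjects per one- or two-dose regimen in Groups 3 and 4 (Protocol 8.5) and the exact Clopper-Pearson interval (SAP shells). Assumption: all 8 are selected, sampled and IgG-positive at the visit. When all n are positive, the lower 95% limit is 0.025^(1/n).

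- None omitted: 8/8, 0.025^(1/8) = 63.1%
- One omitted: 7/7, 0.025^(1/7) = 59.0%
- Two omitted: 6/6, 0.025^(1/6) = 54.1%

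In the by-dose tables, which pool 16 subjects, the same omissions move the lower limit from 79.4% (16/16) to 78.2% (15/15) or 76.8% (14/14).

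The percentage itself can also move. If two of 8 are omitted and 5 of the remaining 6 are positive (83.3%), restoring the two gives between 5/8 = 62.5% and 7/8 = 87.5%, depending on their results.

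**The case against.** The strongest reply is that nothing need be lost. SAP 10.3.1 bases percentages on subjects with data at the visit, section 6.3 summarises observed data, and section 10 uses the full analysis set. A subject selected through Day 91 and bled late qualifies under all three. The programming note may only describe whose samples exist: the IgM template ends at Month 12, so the IgG note has to add the two late visits, and it does not use the word exclude. The footnotes in 10.1.1 and 10.1.2 say who is tested, which the protocol decides in any case.

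This stands as far as it goes. A reader might infer that IgG data are certainly dropped, and the documents do not support that. They support a conflict between the notes and 10.3.1, with omission as the result of one literal reading.

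A reader might also infer that the IgG and VNT rows must differ. That too is conditional. The VNT footnote in 10.1.1 has the same omission, so the rows diverge only if the IgG notes act as a filter and that footnote does not.

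The reply does not remove the mismatch. The Day 91 alternative is part of the protocol's rule, it is absent everywhere the SAP states that rule, and section 12 does not mention it.

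**Conclusion.** The point holds as an undeclared protocol-SAP mismatch with a conditional effect. If the notes are programmed as a filter, subjects eligible under the protocol and measured at Months 18 and 24 fall out of the IgG summary rows, against SAP 10.3.1.

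The reach is limited. The affected tables are exploratory and the trial is descriptive. The VNT shells, which serve a secondary endpoint, carry no restricting note. The shell for listing 16.2.6.2 has no such restriction either, so individual IgG values would still be shown.

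The number affected is not in the documents and may be zero, particularly if Visit 14A samples count as Month 6. A reader might infer that every missed Month 6 visit costs one late IgG value, or might turn a guessed missed-visit rate into subjects lost. Neither is supported: the documents give no such rate, and the Day 91 and Visit 14A conditions both apply. The limits of 59.0% and 54.1% against 63.1% only show the scale for one or two omitted subjects in a fully selected, all-positive regimen of 8.

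**What to change.** Either of two changes removes the conflict:

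- add "or Day 91 if the Month 6 blood sample is not available" to the footnotes in SAP 10.1.1 and 10.1.2 and to the notes for tables 14.2.2.3.1 to 14.2.2.3.4; or
- reword those notes to include all Month 18 and 24 IgG data from full-analysis-set subjects sampled at the visit, in line with 10.3.1, and correct the two footnotes to match the protocol.

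In both cases, state whether a Visit 14A sample counts as the Month 6 sample for selection. The VNT rows need no new filter. If selection on Month 6 alone was intended, declare it in section 12 with a reason.

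The cost is a few lines of SAP text. No new samples are needed, since the protocol already has these subjects bled. The change belongs in an SAP amendment before database lock, because section 6 labels analyses done after SAP finalization as post hoc.
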